- v. As we plan to use an online data format to gather subject information, security of information may be a concern. Fitabase code and databases reside on the Microsoft Windows Azure Platform and rely on the robust security, both physical on-premise guarding, and over network, provided as part of that platform. Windows Azure runs in data centers that comply with key industry standards for security and reliability.
- vi. Loss of confidentiality related to use of protected health information (PHI).

b. BENEFITS

Study subjects may discontinue their participation at any time. However, information regarding the potential benefits to continue on the study will be made explicitly clear prior to their discontinuation.

- i. Whether or not the subject or their family consents, the schedule of the clinic visits will remain the same as proposed in the study. All patients with thrombosis are followed until they become adults with more frequent visits in the first 24 months after the acute event and then yearly afterwards.
- ii. Subjects will also derive benefit from the careful monitoring of activity after thrombosis as well as interval telephone calls to promote compliance and answer questions.
- iii. Successful monitoring after the acute thrombotic event is expected to improve their overall well-being and possibly prevent any physical, cardiac, cognitive and behavioral abnormalities resulting from thrombosis.

- iv. Subjects will be provided with custom fitted compression stockings as part of the study. Compression stockings help to relieve swelling and pain and reduce the risk of developing post-thrombotic syndrome after a DVT. Although prescribed for all post DVT patients, many do not use them due to the expense of the stockings and lack of availability.
- c. Every effort will be made to retain study subjects in the trial for the entire ~9 months to enable complete follow-up and data collection.

V. WITHDRAWAL/TERMINATION

- a. Subjects that 'No Show' for Visit 2, are unable to provide >80% of the 'steps/day' data and are unable to be contacted/rescheduled. Data already collected will be used in the analysis.
- b. Subjects for whom an alternative diagnosis discovered.
- c. In the investigator's medical opinion, it is best to withdraw the subject from the protocol

VI. CONCOMITANT CARE

- a. Patients who initially receive thrombosis care elsewhere prior to enrollment may participate in the study if all eligibility criteria are met.

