Analyses: The objectives of this trial are to assess the feasibility of the design and to measure the effect size of the intervention. All analyses will therefore be descriptive and will be performed once, at the end of the trial. Means and standard deviations, or when appropriate, medians and semi-inter-quartile ranges will be used to describe demographic and clinical characteristics. Reasons for non-eligibility, lack of consent, dropout and lack of compliance will be documented. For feasibility indicators, we (study investigators and [name]-biostatistician) will describe rate of eligibility (proportion of subjects screened who fully meet trial eligibility criteria to participate in the trial), rate of consent (the proportion of eligible subjects who consent to participate) and rate of loss to follow-up (proportion of randomized subjects who drop out of the trial, in total, and by allocated intervention). We will also describe the level of compliance in the intervention group, calculated as the ratio of who complied with the activity prescription to the number given the prescription. We will consider the trial *successful* if the following criteria are met: rate of eligibility $\geq 30\%$, rate of consent $\geq 30\%$, rate of loss of follow-up $<20\%$, level of compliance $\geq 60\%$ and proportion of subjects who complete the trial $\geq 80\%$. For the clinical outcomes (including the secondary outcomes), we will describe change (means and standard deviations) in the intervention and control groups, from baseline to 6 month, in the QoL scores and PTS biomarkers. Each change score will be interpreted for clinical significance and common responses counted for frequency of occurrence. The impact of the activity

Table 2: Feasibility Indicators

Proportion of screened subjects who meet eligibility criteria: $\geq 30\%$

Proportion of screened subjects who provide consent: $\geq 30\%$

Level of adherence in the intervention arm: $\geq 60\%$

Proportion of subjects who complete the trial: $\geq 80\%$

tracker to promote continued physical activity in the last 2 weeks of the 12-week period would be explored. We will also assess the impact of covariates such as age, sex, BMI, baseline activity, intensity of activity over and above the activity prescription, on change scores.

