Sample size calculation: For reasons of practicality and cost, we have decided to limit the size of this pilot RCT to 44 subjects (20 in each arm; 22 after considering a 20% drop out rate). We anticipate that the probable primary outcome for the larger trial will be change in rate of PTS development and/or progression. This trial may also provide compelling preliminary data for future studies. For example, if this intervention reduces the risk of PTS from 26% (known probability of PTS) to 10%, this pilot study has 71% chance of showing a promising trend (p-value<0.2) that the intervention reduces the risk of PTS. We acknowledge that the small size of this pilot study limits the validity of the findings; therefore, we will be cautious with such analyses.

I. RECRUITMENT

- a. Information about the clinical study will be provided via direct communication by study investigators and physicians at Children's Medical Center including ED physicians, hospitalists, and general pediatricians attending on the inpatient medicine services and outpatient continuity clinic as well as house officers.
- b. Information regarding the study will be available on the University of Texas Southwestern clinical trials website and at clinicaltrials.gov.
- c. Potential subjects will be identified through review of new patient referrals to Children's Medical Center, inpatient admissions and/or consultations for thrombosis.
- d. Each subject will receive financial compensation for participation. Payment will be made at completion of the study visits at Visits 1 and 2 (\$25 each) and at the end of Visit 3 (\$50) based on attendance and return of the tracking logs.
- e. Expected recruitment rate will be 2-3 participants per month.
- f. Duration of recruitment period is expected to be approximately 24 months.

- g. Assessment of study recruitment and retention will be performed when 20 participants have been enrolled on the study, or at approximately 9 -12 months.

II. DATA COLLECTION, MANAGEMENT AND ANALYSIS

a. DATA COLLECTION METHODS

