using mean (standard deviations [SD]) for continuous outcomes, and raw counts (%) for categorical outcomes are reported. For the clinical end points, using an intent-to-treat analysis that includes all participants with data at baseline and 6 months (end of the intervention period), within-patient change from baseline (diagnosis or pre-VTE levels) to 6 months (mean, SD) in the physical activity will be compared to standard care in the following measures: D-dimer, FVIII, CRP, thrombin generation assay parameters of endogenous thrombin potential and peak thrombin, fibrinolysis on thromboelastography, QoL (total and physical), selfreported physical activity levels, and PTS (change from 6 to 9 months). This will be averaged for each group, and within-group differences will be compared between the standard care and physical activity groups using a t test. ECS use will be descriptively described but not included in a formal analysis.

ETHICS AND DISSEMINATION

I. RESEARCH ETHICS APPROVAL

This protocol and template informed consent forms will be reviewed and approved UT Southwestern IRB with respect to scientific content and compliance with applicable research and human subjects regulations. Subsequent to initial review and approval, the investigators will submit progress reports to the IRB at least annually and at study closure.

II. PROTOCOL AMMENDMENTS

Any modifications to the protocol, which impact the conduct of the study, or potential risk/benefit of the participants, will require a formal amendment to the protocol with IRB approval.

III. CONSENT OR ASSENT

Informed consent will be obtained after information has been provided to patients' families along with a discussion of the risks and benefits along with opportunity for questions. Consent forms will be provided for all parents involved in the trial.

IV. CONFIDENTIALITY

Records of each patient's participation in this study, including the original informed consent document, will be kept in a locked file cabinet in the Center for Cancer and Blood Disorders at Children's Medical Center. Access to local

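### Randomizing 22 per arm does not leave 20 after a 20% drop-out: that needs 25 per arm, and 44 randomized leaves about 35 completers, not 40

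*Combined protocol and SAP*

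**What the plan says.** The sample size paragraph of section VII (Outcomes and Power Calculations) explains that practicality and budget led the investigators to "limit the size of this pilot RCT to 44 subjects (20 in each arm; 22 after considering a 20% drop out rate". It then illustrates what the pilot might show: if PTS falls from 26% to 10%, "this pilot study has 71% chance of showing a promising trend (p-value<0.2) that the intervention reduces the risk of PTS". No number per arm, test, sidedness or visit is attached to that 71%.

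Three other places bear on the point.

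- **Definition of loss.** The Analyses paragraph of section VII defines loss to follow-up as the "proportion of randomized subjects who drop out of the trial, in total, and by allocated intervention". It sets success at loss below 20% and completion of at least 80%.
- **Length of follow-up.** The retention item (item c under Modifications) promises efforts to "retain study subjects in the trial for the entire ~9 months to enable complete follow-up and data collection". Completion therefore means reaching the last visit.
- **Analysis set.** The Statistical Analyses section uses an intent-to-treat set that "includes all participants with data at baseline and 6 months". It also lists the change in PTS from 6 to 9 months among the comparisons.

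Allocation is 1:1, so 44 randomized is 22 per arm.

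**The concern.** The breakdown reads as a target of 20 evaluable subjects per arm, raised to 22 to absorb a 20% drop-out. A rise from 20 to 22 is far too small for that, and nothing else in the plan explains 22. A reader will expect about 40 completers if 20% are lost, when the plan's own figures give about 35.

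Retention is itself a feasibility criterion, so the sample size statement and the success threshold imply different numbers of completers. The number of subjects behind the PTS illustration is also left unclear.

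**Working it through.** **Inputs.** 44 randomized, 1:1 (22 per arm); 20 per arm to remain; drop-out 20%; loss measured on randomized subjects; PTS risks 26% and 10%; p<0.2. All are in section VII except the allocation ratio, which is under Study procedures/Randomization. Sidedness is not given, so both readings are shown.

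**Step 1: the plan's own figure.** With loss as a share of those randomized, the number to randomize is n/(1 − d):

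- 20/(1 − 0.20) = 25 per arm, 50 in total.
- The cruder add-on n × (1 + d) gives 20 × 1.20 = 24 per arm, 48 in total.

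Neither gives 22 and 44.

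**Step 2: what 22 does cover.**

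- Losses covered: 22 − 20 = 2 per arm, a drop-out of 1 − 20/22 = 9.1%.
- Losses at 20%: 22 × 0.20 = 4.4 per arm.
- 20 × 1.10 = 22, so the figure matches a 10% uplift. It also matches adding 20% of one arm (4 subjects) to the total of 40. Either origin is a guess; the plan does not say.

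**Step 3: completers at 20% loss.**

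- Per arm: 22 × 0.80 = 17.6.
- In total: 44 × 0.80 = 35.2, against the 40 implied.
- Smallest whole number meeting the completion criterion: 36 (36/44 = 81.8%; 35/44 = 79.5%). A trial that only just succeeds on retention would thus end 4 short of 40.
- If each subject independently had a 20% chance of dropping out (an assumption), the chance that at least 40 of 44 complete is about 4%.

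**Step 4: the 6-month analyses.** A subject lost after Visit 2 still has baseline and 6-month data. At 20% total loss the 6-month set is 17.6 per arm if all losses come before Visit 2, and 22 if all come after. This assumes that every completer has the 6-month measurement in question; missing samples or forms would lower it for that measure.

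**Step 5: the 71%.** Pooled two-proportion z test, normal approximation, with mean risk 0.18:

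chance = Φ{[0.16√n − z√(2 × 0.18 × 0.82)] / √(0.26 × 0.74 + 0.10 × 0.90)}

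One-sided z = 0.842. At n = 22 this is Φ[(0.750 − 0.457)/0.531] = 70.9%. The enumeration columns sum exact binomial probabilities over all outcomes for which the same uncorrected test gives p<0.2, with equal arms.

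| n per arm | Pooled z, one-sided | Enumerated, one-sided | Pooled z, two-sided | Enumerated, two-sided |
|---|---|---|---|---|
| 17 | 64.8% | 67.7% | 47.3% | 47.9% |
| 18 | 66.2% | 68.7% | 48.7% | 49.2% |
| 20 | 68.7% | 70.7% | 51.4% | 52.2% |
| 22 | 70.9% | 72.6% | 54.1% | 55.3% |

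At n = 17.6 the one-sided pooled figure is 65.6%. The stated 71% is therefore reproduced one-sided, with 22 per arm by the normal approximation or with 20 per arm by enumeration. The plan does not settle which. Neither method gives 71% at 17 or 18 per arm. Between 20 and 17 or 18 per arm the one-sided figure drops by 2.5 to 3.9 points (pooled z) or 2.0 to 3.0 points (enumeration). No two-sided reading in the table approaches 71%. Fisher's exact test, one-sided, gives only 51% at 20 and 54.5% at 22, so it is not the source either.

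**The case against.** The strongest reply is that the error changes nothing that will be done. The size was set by resources, and the sample size paragraph itself says the small number limits validity and calls for caution. The feasibility criteria are proportions, so none depends on 20 per arm. Enrolment, randomization and analysis would be the same whether the drop-out allowance read 9% or 20%. All of this stands and keeps the point minor. It justifies 44; it does not make the stated allowance correct.

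The 20% may also be a ceiling borrowed from the success criterion, not a forecast. That is a fair reason to write that 17 to 18 per arm *would* complete if 20% were lost, without predicting it. It does not rescue 22, which fails to cover 20% on either reading.

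The analyses may lose fewer subjects than the completer count suggests. The 6-month set keeps those lost after Visit 2, and the Withdrawal/Termination section says data already collected will be used. This stands too. PTS is assessed at both Visit 2 and Visit 3, and the plan does not say which visit the 26% versus 10% comparison uses. At Visit 2 the set could be anywhere from 17.6 to 22 per arm under the condition in step 4. The completer figure applies directly only to outcomes that need Visit 3, such as PTS change from 6 to 9 months.

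Finally, the recalculated chances assume a one-sided test that the plan does not state. That is why the two-sided values are shown as well. The drop-out arithmetic does not depend on sidedness.

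**Conclusion.** The drop-out allowance is wrong as written; the point is minor. Keeping 20 per arm at 20% loss needs 25 per arm (50 in total), not 22 (44). With 44 randomized, 20% loss leaves 17.6 per arm, about 35 completers in total, which is about 5 fewer than the paragraph implies. This rests only on the plan's own numbers and its own definition of loss, and confidence is high.

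The effect on the illustrative PTS chance is secondary. It amounts to about 2 to 4 points between 20 and 17 or 18 per arm, assuming a one-sided test and analysis of completers only. No decision rule uses that chance or the p<0.2 threshold.

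**What to change.** Keep 44 and correct the description, for example: *44 subjects (22 per arm); if 20% are lost, about 17–18 per arm (about 35 in total) would complete the trial.*

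Give the illustrative PTS chance by one named method, with its n, its sidedness and the visit at which PTS is compared. For example: *about 66% with 17–18 completers per arm, 71% with 22 per arm and no loss (pooled two-proportion z test, normal approximation, one-sided p<0.2).* If the 71% came from another method, name it and use it for both figures. If the comparison is at Visit 2, say that the lower figure assumes all losses occur before that visit.

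Replacing 20% with a drop-out allowance of about 9% would also make 20 and 22 agree, but only if the sponsor can justify that rate.

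The cost is a wording change: no extra subjects, and no change to the design or the analyses.

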The parents/legal guardians will be given an explanation about the study and informed consent and/or assent will be obtained. This may occur in the inpatient or the outpatient setting. Demographic information and relevant medical history, including results of scans and thrombophilia testing will be collected. All medications, including anticoagulant medication received for the thrombotic event will be recorded.

a. Baseline Assessments (collected as SOC (standard of care)):

i. History and Physical Examination:

1. Detailed history regarding medical disorders predisposing to thrombosis and potential triggers (birth control pills, recent travel or surgery or immobility) and predispositions (thrombophilia, obesity etc.) will be collected.
2. Review of existing medical records recorded on Children's Medical Center electronic medical record to review past medical, family and social history will be performed.
3. Comprehensive physical exam (PE) consisting of vital signs, general appearance, head, eyes,

ears, nose, throat (HEENT), cardio-respiratory, abdominal, extremities and skin will be performed at each visit as per standard of care.

- ii. Laboratory:
 - 1. Complete blood count (CBC), reticulocyte count, baseline coagulation studies, and a comprehensive thrombophilia panel performed as SOC will be recorded.
- iii. Treatment:
 - 1. Information on anticoagulant therapy (medication of choice, intensity of anticoagulation, planned duration of therapy) prescribed as per the treating physician will be collected for subjects who meet eligibility criteria and whose parents provide written informed consent
- iv. Radiological:
 - 1. All information related to site, extent and venous segments involved of the thrombotic venous segment at the time of diagnosis, and at completion of therapy will be collected. Information on reflux assessment at the time of end of therapy ultrasound will also be collected.
- v. Assessment of **Post-thrombotic syndrome (PTS)**: All subjects will be assessed with standardized, validated outcome assessment tools: the Manco-Johnson Instrument and the modified Villalta scale starting at 6 months post diagnosis of DVT as per standard of care. See appendix 1 for these scales.

b. Study Interventions:

i. Study procedures/Randomization:

Eligible, consenting subjects will be individually randomized via a web-based program to the Fitbit arm or the control arm (1:1 allocation ratio).

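### The dropout arithmetic does not give 20 evaluable per arm, and the 71% chance for PTS needs an unstated one-sided p and 20 to 22 analysed per arm; with 20% dropout it is about 66–69%

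*Combined protocol and SAP*

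**What the plan says.** The sample size paragraph in section VII (Outcomes and Power Calculations) limits the pilot, for practicality and cost, to "44 subjects (20 in each arm; 22 after considering a 20% drop out rate"). It then gives one worked example: "if this intervention reduces the risk of PTS from 26% (known probability of PTS) to 10"%, then "this pilot study has 71% chance of showing a promising trend (p-value<0.2"). The trend is described in one direction, as "a promising trend (p-value<0.2) that the intervention reduces the risk of PTS". The paragraph does not name the test, say whether the p-value is one- or two-sided, or say whether 20 or 22 per arm lies behind the 71%.

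Three other places bear on this:

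- Randomization is "to the Fitbit arm or the control arm (1:1 allocation ratio"), so 44 subjects means 22 per arm.
- The Statistical Analyses section says that the clinical analysis "includes all participants with data at baseline and 6 months (end of the intervention period"). Subjects who leave without 6-month data therefore reduce the analysed number.
- The only test named there is for change scores: "within-group differences will be compared between the standard care and physical activity groups using a t test". No test of PTS proportions is specified.

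**The concern.** The paragraph gives a dropout rate, an evaluable number and a randomized number that cannot all be true together. It then states a chance of success without saying which number it uses. If the 20% dropout rate is the planning assumption, fewer than 20 per arm will be analysed and 71% is too high. A reader also cannot tell from the text that the p-value must be one-sided for the figure to hold.

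This is the only power figure in the plan. It supports the statement that the pilot may yield useful preliminary data on PTS, the outcome that the investigators expect to be primary in the larger trial. Someone planning that trial should be able to see what the figure assumes.

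**Working it through.** **Inputs.** From the sample size paragraph: p1 = 0.26, p2 = 0.10, threshold p < 0.2, 22 randomized per arm, 20 per arm labelled evaluable, 20% dropout. From the randomization paragraph: 1:1 allocation. The test and the sidedness are not given, so several standard choices were tried.

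**Step 1: dropout arithmetic.**

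- 20% loss from 22: 22 × 0.80 = 17.6 per arm (44 × 0.80 = 35.2 in total, so 17 or 18 per arm).
- Loss implied by 22 to 20: 1 − 20/22 = 9.1%.
- Number needed to keep 20 after a 20% loss: 20/0.80 = 25 per arm, or 50 in total.

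**Step 2: reproduce the 71%.** Pooled normal approximation for two proportions:

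power = Φ{ [ (p1 − p2) − z·√(2·p̄(1 − p̄)/n) ] / √( (p1(1 − p1) + p2(1 − p2))/n ) }, with p̄ = 0.18 and z = 0.8416 for a one-sided 0.2.

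- n = 22: (0.16 − 0.8416 × 0.11584)/0.11330 = 0.06251/0.11330 = 0.552, so power = **70.9%**.
- n = 20: (0.16 − 0.8416 × 0.12149)/0.11883 = 0.486, so power = 68.7%.
- n = 17.6: (0.16 − 0.8416 × 0.12951)/0.12667 = 0.403, so power = 65.6%.

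Exact enumeration sums the binomial probabilities of every pair of counts for which the uncorrected one-sided z test gives p < 0.2. At n = 20 it gives **70.7%**, which also rounds to 71%.

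**Step 3: one-sided results by method (uncorrected tests).**

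| Analysed per arm | Pooled normal | Unpooled normal | Arcsine | Exact z test |
|---|---|---|---|---|
| 22 | 70.9% | 71.6% | 71.7% | 72.6% |
| 20 | 68.7% | 69.3% | 69.4% | 70.7% |
| 18 | 66.2% | 66.8% | 66.9% | 68.7% |
| 17.6 | 65.6% | 66.3% | 66.4% | – |
| 17 | 64.8% | 65.5% | 65.6% | 67.7% |

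With 20 analysed per arm the answer is about 69–71%. With a 20% loss it is about 66–69%: 65.6–66.9% by the normal formulas at 17.6 to 18 per arm, and 67.7–68.7% by the exact z test at 17 and 18. No method reaches 71% at 17 or 18 per arm.

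**Step 4: sidedness.** With z = 1.2816 (two-sided 0.2), the pooled formula gives 54.1% at 22, 51.4% at 20 and 48.1% at 17.6 per arm. Across the uncorrected methods the two-sided figure at 20 per arm is about 51–53%, and at 22 or fewer per arm it is never above about 55%. The 71% therefore rests on a one-sided p.

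**Step 5: choice of test.** A one-sided Fisher exact test gives 54.5% at 22 per arm and 51.0% at 20. The documents do not name that test, so these values show only that the figure depends on the test as well as on n.

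**Step 6: no effect.** With the same risk in both arms, the one-sided z test at 20 per arm gives p < 0.2 in 19.5% of trials at a common risk of 26%, 20.4% at 20% and 23.4% at 10% (exact enumeration), so about 20%.

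**The case against.** The strongest defence is that 71% is a correct answer for the evaluable number that the plan itself states: the exact one-sided z test at 20 per arm gives 70.7%. This stands. A reader might infer that the 71% was computed on all 22 per arm and ignores dropout. The documents do not show that, because they name neither the test nor the n, and both 20 and 22 per arm can give 71%.

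A reader might also infer that the real chance is about a coin toss, since a two-sided p gives 51–53% at 20 per arm. The documents do not support that either. The sentence concerns a reduction in risk, so a one-sided p is its natural reading. Leaving out the word is an omission in reporting, not a wrong calculation, and the two-sided value is a sensitivity note.

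Finally, little depends on the figure. It is offered as an example, the size was fixed on other grounds, PTS is secondary, success is judged by feasibility criteria, analyses are described as descriptive, and the authors promise caution. This stands too and keeps the point minor.

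The defence does not remove the conflict between 20% dropout and 20 evaluable from 22. The feasibility criteria accept 80% completion, so a loss of that size is one that the plan tolerates.

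**Conclusion.** Two defects hold, and both are minor. The stated 20% dropout and the stated 20 evaluable per arm are inconsistent with 22 randomized per arm. The 71% holds for a one-sided p and 20 to 22 analysed per arm, neither of which is stated alongside it. At the plan's own 20% dropout the chance is about 66–69%, some 2 to 5 points lower.

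This rests on the plan's risks of 26% and 10%, an uncorrected two-proportion z test, equal loss in the two arms, and dropouts having no PTS data. If the intended dropout is about 9%, 20 per arm is right and the chance is about 69–71%, so only the percentage label and the missing description of the test need correcting.

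**What to change.** First, correct the dropout arithmetic in the sample size paragraph. Either state about 9% dropout with 20 evaluable per arm, or keep 20% dropout with about 17 to 18 evaluable per arm.

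Second, restate the power sentence with the test, sidedness and evaluable number. For example: *With a one-sided p<0.2 (uncorrected two-proportion z test), the chance is about 69–71% with 20 analysed per arm and about 66–69% if 20% of the 44 drop out; with no effect this rule is met about 20% of the time.* The two-sided figure, about 51–53% at 20 per arm, may be added as a sensitivity note.

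The cost is a corrected parenthesis and one rewritten sentence. If 20% dropout is kept, the quoted chance becomes slightly less favourable. Sample size, visits and conduct do not change.

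### Feasibility success is read from bare percentages, so one child can flip the adherence or retention verdict, and the 20% planning dropout fits neither the loss criterion nor the step from 20 to 22 per arm

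*Combined protocol and SAP*

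**What the plan says.** In the combined protocol and SAP, section VII (Outcomes and Power Calculations), the Analyses paragraph declares the trial successful "if the following criteria are met: rate of eligibility" and four further rates each reach a cut-off. The five cut-offs are eligibility at least 30%, consent at least 30%, loss to follow-up below 20%, compliance at least 60% and completion at least 80%. Table 2 repeats four of them. Loss is counted among randomised subjects. Compliance is counted among those given the activity prescription, which is set after four weeks of baseline wear.

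Section II.c (Statistical Analyses) says the feasibility outcomes are descriptive and that "raw counts (%) for categorical outcomes are reported". No section gives a confidence interval, an error rate or an assumed true rate for any criterion.

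The sample size paragraph fixes the trial at 44 children: "20 in each arm; 22 after considering a 20% drop out rate". Randomisation is "to the Fitbit arm or the control arm (1:1 allocation ratio"), so the Fitbit arm has 22.

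**The concern.** Feasibility is one of the two primary outcomes, and the success rule is the only place where the plan turns it into a conclusion. For two of the criteria the numbers are small enough that the rule responds to a single child. A report giving only the count, the percentage and the word successful would not show that the data are compatible with rates well on either side of the cut-off.

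The dropout figures also conflict. The same 20% is the planning allowance in one paragraph and the start of failure in another, and the inflation actually applied does not correspond to 20%. A reader cannot tell how many evaluable children the investigators expect, or how likely they think the retention criterion is to be met.

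**Working it through.** **Inputs from the documents.** 44 randomised, 22 per arm, 20 per arm evaluable, 20% dropout; compliance at least 60%; loss below 20%; completion at least 80%.

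**Assumptions.** Each child is adherent or not (the plan gives no clear per-child definition). All 22 Fitbit children receive the prescription unless stated. A child who does not complete is a child lost. True rates are not in the documents, so a range is shown.

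**1. The plan's own probability.** The plan states no operating figure for feasibility. Its only one is a "71% chance of showing a promising trend (p-value<0.2") if the intervention "reduces the risk of PTS from 26% (known probability of PTS) to 10"%. With n per arm and a pooled normal approximation, power = Φ[(0.16 − 0.8416·SE0)/SE1]. For n = 22, SE0 = √(2·0.18·0.82/22) = 0.1158 and SE1 = √((0.26·0.74 + 0.10·0.90)/22) = 0.1133, so power = Φ(0.552) = 70.9%. The 71% is therefore reproduced one-sided with 22 per arm. With 20 per arm the same formula gives 68.7%, although an exact enumeration of the z test gives 70.7%, so the match does not prove which n was used. It says nothing about feasibility.

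**2. Pass marks.**
- Adherence: 0.60 × 22 = 13.2, so 14 are needed (13/22 = 59.1% fails).
- Retention: 0.20 × 44 = 8.8, so at most 8 may be lost. Equivalently, 0.80 × 44 = 35.2, so 36 must complete (35/44 = 79.5% fails).

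**3. Exact 95% intervals at the marks.** Clopper-Pearson: lower = Beta(0.025; x, n−x+1), upper = Beta(0.975; x+1, n−x).

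| Result | Estimate | 95% CI | Verdict |
|---|---|---|---|
| 14/22 adherent | 63.6% | 40.7-82.8% | pass |
| 13/22 adherent | 59.1% | 36.4-79.3% | fail |
| 36/44 complete | 81.8% | 67.3-91.8% | pass |
| 35/44 complete | 79.5% | 64.7-90.2% | fail |

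By the same formula, the lower limit first exceeds 60% at 19/22 (65.1%; 18/22 gives 59.7%) and first exceeds 80% at 41/44 (81.3%; 40/44 gives 78.3%).

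**4. Adherence criterion: chance of failing, P(X ≤ 13), X ~ Bin(22, p).**

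| True adherence (assumed) | 60% | 65% | 70% | 75% | 80% |
|---|---|---|---|---|---|
| Fails | 55% | 35% | 19% | 7% | 2% |

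In the other direction, if half the children truly adhere, P(X ≥ 14 of 22) = 14%, and with 20 evaluable P(X ≥ 12 of 20) = 25%.

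**5. Retention criterion: chance of passing, P(Y ≤ 8), Y ~ Bin(44, d).**

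| True dropout | 20% | 15% | 10% | 9.1% |
|---|---|---|---|---|
| Passes | 47.0% | 79.4% | 97.2% | 98.4% |

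At the stated planning value of 20%, the criterion is missed 53% of the time.

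**6. The inflation step.** 1 − 20/22 = 9.1%. Keeping 20 per arm after 20% loss needs 20/(1 − 0.20) = 25 per arm. Starting from 22, 20% loss leaves 22 × 0.80 = 17.6 per arm.

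**7. Eligibility and consent.** These use screened or eligible children. If consent is 30% of eligible children, 44 consenting implies 44/0.30 ≈ 147 eligible; if eligibility is also 30%, 44/0.30/0.30 ≈ 489 screened. (The text uses eligible subjects as the consent denominator; Table 2 uses screened subjects.)

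**The case against.** Several objections have force. The trial is a pilot, its analyses are declared descriptive, and raw counts let any reader compute an interval. The sample size paragraph concedes that small size limits validity, and recruitment and retention are to be assessed once 20 participants are enrolled. But description does not dispose of the point, because the plan adds a yes/no verdict to it. The concession about size directly follows the PTS calculation and leaves the success rule unchanged.

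Any cut-off placed at the true rate gives roughly a coin toss, so the 47/53 split is close to inevitable once 20% is taken as the truth. An allowance for dropout may also be the worst tolerable loss rather than the expected one. That stands: the split shows a conflict only if 20% is what the investigators expect, and the plan does not say. The mismatch between 20% and the step from 20 to 22 remains on either reading.

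A reader might infer that a workable regimen fails about one time in three. The documents do not support a single figure. It arises, for example, at 70% adherence with 15% loss (0.814 × 0.794 = 0.646 passing both), but neither rate is in the plan, and multiplying treats overlapping children as independent. On the same basis, failing either criterion ranges from 10% (75% adherence, 10% loss) to 70% (65%, 20% loss).

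**Conclusion.** The point holds for adherence and retention. The success verdict there can turn on one child while the intervals almost coincide, and the plan states neither that uncertainty nor the resulting error rates. Failure on adherence runs from 55% to 2% as assumed true adherence goes from 60% to 80%; a regimen that half the children follow passes 14-25% of the time. These figures rest on a yes/no status per child and on the stated denominators. The dropout conflict is in the plan's own numbers: 20% is both planned for and counted as failure, and the sample size allows for only 9.1%.

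Two wider readings are not supported. The whole verdict does not rest on 22 to 44 children, because eligibility and consent have larger denominators. Nor does the plan say that missing a criterion ends the programme; it says only whether the trial will be considered successful.

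**What to change.** - In section II.c, report every feasibility indicator with an exact 95% CI beside the count and percentage, naming its denominator.
- In section VII, keep the present thresholds, but state the success verdict together with whether each CI excludes its threshold.
- Add a short table of pass probabilities over a stated range of true adherence and dropout rates, with the per-child definition of adherence it assumes.
- Reconcile the sample size paragraph with the loss criterion. Either restate the dropout that 44 randomised allows for (about 9%), or give the evaluable number expected at 20% loss (about 17-18 per arm). Say whether 20% is the expected or the worst tolerable loss.

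The cost is wording and simple calculation, with no extra children, visits or data. The downside is that the verdict will look less certain: with 22 and 44 children, a CI lies wholly above its threshold only from 19/22 adherent or 41/44 completing. The stated evaluable number or dropout allowance will also look less favourable. Three-band criteria (proceed, amend, stop) are an option but not part of the required change; keeping the present cut-off as the top line would leave the 14-25% false-pass rate as it is.
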